## **9.3 Differentiation of malaria re-infections and recrudescences**

DNA from dried blood spots will be used for molecular characterisation of the parasite using polymorphisms in the *msp1*, *msp2* and CA1 polymerase genes [22]

## **9.4 Detection of mutations in the *csp* gene of *P. falciparum***

DNA will be extracted from selected blood spots collected from children with malaria and analysed for mutations at the Th2 or Th3 locus of the *csp* gene of *P. falciparum* associated with evidence of reduced efficacy following RTS,S/AS01E vaccination [17] These assays will be conducted at the Broad Institute, Boston.

## **9.5 Measurement of haemoglobin concentration**

Haemoglobin concentration will be measured colorimetrically using a Hemocue colorimeter (Hemocue AB, Angelholm, Sweden).

## **9.6 Measurement of anti-CSP concentration**

Antibodies to CSP will be measured by a standardised ELISA used in many previous trials of RTS,S/AS01E at the University of Ghent [23]

## **9.7 Measurement of a broad range of malaria antibodies.**

Antibodies to a broad range of malaria antigens will be measured using the Luminex assay at LSHTM.

## **9.8 Measurement of malaria parasitaemia using a novel 18S rRNA/rDNA biomarker**

Testing for malaria parasite DNA will be undertaken in a sub-set of samples by [name] at the University of Washington, Seattle, USA.

# **10. STATISTICAL CONSIDERATIONS**

## **10.1 Statistical analysis plan**

All data will be collected and verified prior to analysis. Detailed statistical procedures, listings, table shells, and figures will be provided in a statistical analysis plan (SAP) prior to analysis. The SAP will be finalized before study close-out and database lock and will be submitted to the DSMB before the study code is broken.

The following key statistical components and a detailed description will be documented in the SAP:

- Primary and secondary endpoints and how they will be measured.
- Statistical methods and tests that will be used to analyze the endpoints.
- Indication of whether the comparisons will be using one-tailed or two-tailed tests (with justification of the choice) and the level of significance to be used.
- Identification of whether any adjustments to the significance level or the overall p value will be made to account for any planned or unplanned subgroup analyses or multiple testing
- Specification of potential adjusted analyses and a statement with which covariates or factors will be included.
- Planned exploratory analyses and justification of their importance.

The number of subjects enrolled, vaccinated, completed, or withdrawn will be summarized. Reasons for withdrawal, when known, will be provided. Demographic data will be summarized by descriptive statistics and will include total number of observations (n), mean, standard deviation (SD) and range for continuous variables, and number and percentages for dichotomous variables.

All the investigators involved in the collection of clinical or laboratory data will be blind as to which group the individual study children have been allocated. However, based on the likely final results from the first phase of the trial the investigators are likely to know that none of the study groups was significantly inferior to another and it could be argued that this could influence how data are collected and analysed (anti-conservative bias). However, the investigators consider that this risk is small. The trial statistician undertaking the analysis of the initial phase of the study will need to be able to link study findings to an individual child but measures will be undertaken to enable this to be done without the statistician being unblinded for the period of the extension. This will be done by developing a second set of IDs for the trial participants with only the independent trial statistician knowing how the numbers link to the child's initial number and study group. In this way, during the course of the extension study, the trial statistician dealing with data related to an individual child will not know the identity of the trial group to which that child belongs.

## **10.2 Sample size and analysis of the primary efficacy endpoint**

At a survey conducted in April 2019, 5363 of the 5887 (91%) children enrolled in the first phase of the trial were contactable, an annual loss of about 5%. Assuming that this rate of attrition continues for a further year and that a similar proportion of families do not consent for their child to join the extension study, it is likely that approximately 4,800 children will enter the extension study.

The primary analyses will cover the entire study period, ie. the initial three years of the study and the two year extension period. The entire study period is defined as the time from enrolment in June 2017 until the end of the study year in which the child reaches five years of age and is no longer eligible for SMC, i.e. between 5 and 20 months of age (depending upon the exact age at first vaccination) and 60-71 months of age (depending upon the timing of the child's fifth birthday in relation to the SMC schedule). On the basis of date of enrolment, the exit dates above, and losses to follow-up as described above, we estimate that there will be approximately 20,625 person-years of follow-up during the entire study period: 6875 person-years per study group (i.e. an average of 3.5 person-years per child originally recruited).

The primary end-point for the trial is the incidence of clinical episodes of malaria. Based on data from the first two years of the ongoing study, we assume that the incidence of malaria will be 200 cases per 1000 children per year over the entire study period. Based on this assumption, the study will have 90% power to detect a 12.0% or greater relative difference (absolute difference: 24 cases per 1000 child-years) between the RTS,S/AS01E + SMC and the RTS,S/AS01E alone or SMC alone groups, through a standard superiority comparison.

The study will also have 90% power using a two sided 95% confidence interval to exclude a 17.5% relative difference (absolute difference: 35 cases per 1000 child-years) in incidence of clinical malaria between children in the RTS,S/AS01E alone or SMC alone group, using a non-inferiority design, over the entire study period. To determine the level of confidence with which this margin can be excluded, we will also calculate two sided 90% and 99% confidence intervals.

There will be approximately 4,100 child-years of observation in the year following the third booster; 1367 child-years in each study group. Assuming the incidence of clinical episodes of malaria remains at about 200 episodes per 1,000 children per year during this period, the study will have 90% power, through a standard superiority comparison, to detect a 25.9% or greater relative difference (absolute difference: 52 cases per 1000 child-years) between the RTS,S/AS01E + SMC and the RTS,S/AS01E alone or SMC alone group. In the same period, the study will have 90% power, using a two sided 95% confidence interval, to exclude a 39.2% relative difference (absolute difference: 78 cases per 1000 child-years) in the incidence of clinical malaria between children in the RTS,S/AS01E alone or SMC alone group, using a non-inferiority design.

A similar analysis will be undertaken for the final year of the study following administration of a fourth booster dose of the RTS,S/AS01E or comparator vaccine but study power will be reduced because slightly more than half of the children enrolled (3860/5920) will not be eligible for SMC in 2021-22, and thus will not contribute further events nor person-time at risk to the study period.

Both intention-to-treat and per-protocol analyses will be undertaken. Children who received any dose of SMC or vaccine will be included in the intention to treat analysis. Children who received all scheduled doses of SMC, or who were treatment for a clinical episode of malaria at a time when SMC would have been given, or all scheduled doses of vaccine will be included in the per protocol analysis for each year of the study. Results obtained in Burkina Faso and Mali will be analysed separately. Additional sub-analyses will include analysis by age, gender, and bed net use during the transmission season, as determined by the history obtained at the cross-sectional surveys.

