### **Analyses in individual years**

There will be approximately 4,100 child-years of observation in the year following the third booster; 1367 child-years in each study group. Assuming the incidence of clinical episodes of malaria remains at about 200 episodes per 1,000 children per year during this period, the study will have 90% power, through a standard superiority comparison, to detect a 25.9% or greater

relative difference (absolute difference: 52 cases per 1000 child-years) between the Combined RTS,S/AS01E + SMC group and the RTS,S/AS01E alone or SMC alone group.

A similar analysis will be undertaken for the final year of the study following administration of a fourth booster dose of the RTS,S/AS01E or comparator vaccine but study power will be reduced because slightly more than half of the children enrolled (3860/5920) will not be eligible for SMC in 2021-22, and thus will not contribute further events nor person-time at risk to the study period.

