### Primary endpoint

#### Hazard Ratios

The hazard ratio for the primary outcome will be estimated using Cox regression models, with a robust standard error (i.e. the Andersen-Gill extension of the Cox model) to account for potential clustering of episodes within children. The Efron method will be used for tied event times.

The timescale will be calendar time. For analyses of the whole study period, calendar time will start from 1st April 2017, i.e. allowing delayed entry according to the precise timing of the first vaccination contact. This ensures that risk sets in the Cox models are comparable with respect to the timing of onset of transmission each year, and the timing of SMC. Due to variable timing in vaccine dose 1 in 2017, this would not be the case if the data were analysed on the time in study timescale. For the same reasons, analyses of the effectiveness of the sixth and seventh doses of RTS,S, calendar time will start from 1st April 2020 and 1st April 2021, respectively (i.e. the beginning of the study year in which the sixth and seventh doses were administered).

Nelson-Aalen Cumulative hazards will be plotted for each group to show the mean number of events per child during the study and the timing of events, and Kaplan Meier failure estimates will be plotted to show the risks during the study.

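### The superiority power figures (12.0% over the whole period, 25.9% in year 4) assume independent episodes, while the planned analysis allows for clustering and the neighbouring non-inferiority figures match twice that variance

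*Combined protocol and SAP*

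**What the plan says.** Protocol section 10.2 bases the whole-period calculation on "6875 person-years per study group", described as "an average of 3.5 person-years per child originally recruited", and on this rate: "we assume that the incidence of malaria will be 200 cases per 1000 children per year over the entire study period". From these it concludes that "the study will have 90% power to detect a 12.0% or greater relative difference" ("absolute difference: 24 cases per 1000 child-years") between the combined group and either single-intervention group. For the year after the third booster, with 1,367 child-years per group and the same rate, it claims 90% power "to detect a 25.9% or greater relative difference". The SAP repeats the two superiority statements under Superiority Comparison and Analyses in individual years ("There will be approximately 4,100 child-years of observation in the year following the third booster").

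Neither document attaches an overdispersion, frailty or design-effect term to these figures. The same protocol section gives non-inferiority differences of 17.5% (whole period) and 39.2% (year 4) at 90% power. Section 10.3.4 gives 29.6% (90% power) and 25.6% (80% power) for the rebound comparison. These also state no variance factor.

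For the analysis, the SAP (Study outcomes, Primary Endpoint) discards an episode only if it falls within 7 days of a previous one. Under Hazard Ratios it specifies an Andersen-Gill Cox model with a robust standard error "to account for potential clustering of episodes within children".

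**The concern.** A power statement should use the variance of the analysis it describes. If some children are more prone to malaria than others, the number of episodes per child varies more than a Poisson count. The robust standard error will then exceed the Poisson one, and power at a given difference will be lower than stated. The protocol does allow for clustering elsewhere: section 10.3.1 uses an intra-cluster correlation of 0.1 and a design effect of 1.9 for the school survey.

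There is also a problem of internal consistency. Superiority and non-inferiority figures stand side by side for the same endpoint, rate and person-time. If they rest on different variances, a reader cannot compare the precision claimed for the two co-primary questions.

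**Working it through.** **Inputs.** Rate 0.200 per child-year; 6,875 child-years per group (whole period) and 1,367 (year 4); 20,625 child-years over 5,887 children = 3.50 years per child (protocol 10.2). Rebound: 0.600 per child-year, 800 child-years per group (10.3.4). The superiority text states neither alpha nor sidedness. The SAP's multiplicity section sets 5% for pairwise tests. I take two-sided 5%, because it reproduces the figures; one-sided 5% gives about 94.5% power.

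**Step 1: reproduce the superiority figures.** Power = Φ(|r0 − r1| / √[D(r0 + r1)/PY] − 1.96), where D is a variance factor and D = 1 means independent Poisson episodes.

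- Whole period: 0.024 / √(0.376/6875) = 0.024/0.007395 = 3.245; power 90.1%. The difference detectable with 90% power is 11.99%.
- Year 4: 0.0518 / √(0.3482/1367) = 0.0518/0.01596 = 3.246; power 90.1%. Detectable difference 25.9%.

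The implied D is 1.00 both times.

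**Step 2: reproduce the non-inferiority and rebound figures.** Under equal rates, excludable difference = (1.960 + z) × √(2Dr/PY), with z = 1.282 for 90% power and 0.842 for 80%.

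| Figure | Stated | D = 1 | D = 2 |
|---|---|---|---|
| Whole period, 90% | 17.5% | 12.4% | 17.5% |
| Year 4, 90% | 39.2% | 27.7% | 39.2% |
| Rebound, 90% | 29.6% | 20.9% | 29.6% |
| Rebound, 80% | 25.6% | 18.1% | 25.6% |

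All four match D = 2.00 on the rate-difference scale with equal rates.

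**Step 3: superiority with clustering (assumed values).** No dispersion value is given, so I use a gamma frailty with variance k and equal follow-up per child. With m expected episodes per child and n children per group, the variance of the group mean is (m + km²)/n. Whole period: m = 0.2 × 3.503 = 0.70 and n = 6875/3.503 = 1,962. Year 4: m = 0.2 and n = 1,367. The last row instead applies the factor from step 2 directly.

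| Assumption | Whole-period power at 12.0% | Detectable | Year-4 power at 25.9% | Detectable |
|---|---|---|---|---|
| k = 0.25 | 85% | 12.9% | 89% | 26.4% |
| k = 0.5 | 80% | 13.8% | 88% | 26.9% |
| k = 1.0 | 71% | 15.3% | 85% | 27.9% |
| D = 2 | 63% | 16.7% | 63% | 35.6% |

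For the same k, year 4 moves less because a child has fewer expected episodes in one year: 1 + km is 1.20 at k = 1.0, against 1.70 over the whole period.

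**Step 4: do the conclusions depend on this?**

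- Superiority at a 60% reduction and D = 3, year 4: 0.12 / √(3 × 0.28/1367) = 4.84; power 99.8%. Over the whole period it is above 99.9%.
- Non-inferiority at 1.20 and D = 2, whole period, log scale with 1,375 expected episodes per group: ln 1.2 / √(2 × 2/1375) = 0.1823/0.0539 = 3.38; power 92%. On the rate-difference scale it is 96%.

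**The case against.** The strongest reply is that the SAP already answers the practical question. It labels its calculations illustrative and treats 200 per 1000 as a floor, against 305 per 1000 observed with SMC alone over three years. It also notes a reduction of about 60%, far beyond 12%. At 305 per 1000, power for 12% would be 98% at D = 1, 91% at D = 1.5 and 81% at D = 2. The 305 is an upper case, because the SAP expects incidence to fall with age.

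Year-4 follow-up may also exceed the plan. Consents total 2,410 + 2,624 = 5,034, or at most 1,678 child-years per group before losses. At that ceiling with k = 1.0, 0.0518 / √[(0.2400 + 0.1702)/1678] = 3.31, so power at 25.9% is about 91%. The SAP speaks only of potential clustering, and the robust standard error protects validity whatever its extent.

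All of this stands, and it settles the consequence. It does not make the printed figures correct at their own printed inputs, nor explain the two variances. A conservative rate is a separate allowance from a variance assumption.

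A reader might go further and infer that the non-inferiority comparison is short of information. The documents do not support that: its figures already match a variance above the 1.70 that k = 1.0 implies. A reader might also take the factor of 2 as the investigators' estimate of overdispersion. The documents do not say so, and it could equally come from a different formula.

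**Conclusion.** The point holds as a mismatch in the stated figures. At the stated rate and person-time, any positive between-child heterogeneity puts superiority power at 12.0% and 25.9% below 90%. The superiority figures are also inconsistent with the non-inferiority and rebound figures, which match twice the variance.

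The size of the shortfall is unknown. The values in step 3 rest on assumed frailty variances, or on carrying the unexplained factor of 2 across, so they are illustrations and not replacement text. The independence assumption is itself inferred from exact reproduction; the documents do not state it.

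It would be tempting to conclude that the trial is underpowered. That does not follow: power for an effect near 60% remains very high, and whole-period non-inferiority power at 1.20 stays at or above 92% at a factor of 2. Estimates, tests and confidence intervals are unaffected.

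**What to change.** Estimate the overdispersion from the blinded, pooled distribution of episodes per child in the first three years, within country because the analysis stratifies on it. The variance factor is 1 + (mean episodes per child) × (frailty variance).

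Pooling over groups adds the treatment effect to the apparent heterogeneity. With relative rates of 1, 1 and 0.4 (assuming equal single-intervention groups and a 60% reduction), the mean is 0.8 and the variance 0.08, which adds 0.08/0.64 = 0.125 to the frailty variance. Either subtract this or have the independent statistician supply a within-group value.

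Apply the same variance assumption to the superiority, non-inferiority and rebound calculations. State the assumption, the alpha and the sidedness, and restate the detectable differences in protocol 10.2 and 10.3.4 and in the two SAP sections. If the factor of 2 was deliberate, say where it comes from.

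The cost is one tabulation of existing data and about one paragraph of text. The superiority figures will look somewhat less favourable. The design, the sample and the 1.20 margin need no change.

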## 4. STUDY DESIGN AND ENDPOINTS

### 4.1 Study areas

The trial will be conducted in Houndé health district, Burkina Faso and in Bougouni district, Mali. The Houndé district is situated 300 km from Ouagadougou and 100 Km from Bobo-Dioulasso where the CHUSS, the 2nd National Reference Hospital (University Hospital), is located and which is the also a base of the Institut de Recherche en Sciences de la Santé, Direction Régionale (IRSS). The study site in Mali is the district of Bougouni in the region of Sikasso, Mali, 150 km south of Bamako where the Malaria Research and Training Centre (MRTC) is based.

**Figure 1** : Map of Mali and Burkina Faso showing the two study sites Bougouni and Houndé.

The population of Houndé district belongs primarily to the Bwaba ethnic group and that of Bougouni primarily to the Bambara and Fula ethnic groups. Farming is the main occupation in each area. Each district has a district hospital.

Malaria, due predominantly to *P. falciparum*, is highly seasonal in both districts with over 80% of cases occurring during the rainy season (July – October) and during the following month. The prevalence of *P. falciparum* malaria in school age children in December 2018 was 24% in Bougouni and 61% in Houndé. The main malaria vector in each study area is *Anopheles gambiae* ss. A high proportion of children sleep under an LLIN. The first line treatment for malaria in the public health system is artemether/lumefantrine in each district. Cases of uncomplicated malaria are treated at one of the health centres in the district and in Bougouni some cases are treated in the community by trained community health workers. Cases of severe malaria are managed in the district hospital.

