### **7.6.3 Prevalence of malaria parasitaemia and anaemia.**

A survey of all study children will be undertaken approximately one month after the last round of SMC administration at the end of each malaria transmission season. Temperature will be measured and any child who is febrile or who has other features suggestive of a diagnosis of malaria will have an RDT done; those who are positive will be treated with artemether/lumefantrine. Finger prick blood samples will be collected for preparing blood slides and filter paper blood spots. The prevalence of parasitaemia, including the presence of gametocytes, will be detected by microscopy.

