### **2.3 Outcomes measured at cross-sectional surveys at the end of the malaria transmission season**

For each of the outcomes below, results will be analysed and presented separately for the two surveys conducted during the extension study (conducted in November/December 2020 and November/December 2021).

- 2.3.1 The prevalence of asexual stage *P. falciparum* infection of any density
- 2.3.2 The prevalence of asexual stage *P. falciparum* infection with density  $\geq 5000$  per  $\mu\text{l}$
- 2.3.3 The prevalence of sexual stage *P. falciparum* infection (i.e. gametocytes)
- 2.3.4 The arithmetic mean *P. falciparum* parasite density, including samples which are parasite negatives as having a density of zero.
- 2.3.5 The prevalence of asexual stage infection of non-falciparum *Plasmodium* species.
- 2.3.6 The prevalence of sexual stage infection (i.e. gametocytes) of non-falciparum *Plasmodium* species.
- 2.3.7 The mean haemoglobin concentration in g/dL.
- 2.3.8 The prevalence of anaemia, defined as measured Hb  $< 10$  g/dL.
- 2.3.9 The prevalence of moderate anaemia, defined as measured Hb  $< 7$  g/dL.
- 2.3.10 The prevalence of severe anaemia, defined as measured Hb  $< 5$  g/dL.

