### Incidence rate differences

In addition to the hazard ratios from Cox regression, as described above, the incidence rate differences (IRD) will also be calculated, i.e. the cases averted per 1000 child-years at risk. This is recommended in the updated CONSORT guidelines (8), as this gives an indication of the reduction in incidence attributable to the interventions, i.e. the absolute public health impact in similar contexts. This is an important question for the overall effect of the two interventions under study in this trial, which is a question of key interest for policy makers. This is also relevant to the interpretation of efficacy over successive years of the study. For example, if the hazard ratio between the intervention groups moves towards unity as children become older, but malaria incidence increases in older children, the absolute impact of the interventions could remain as important (or even more important), in older children. Alternatively, if the hazard ratio remains similar to that seen in the initial intervention period but incidence falls in older children, extension of vaccination into older children may not be warranted.

The IRD will be calculated using ordinary least squares regression of transformed variables for the intervention group, country and person-time at risk, as described by Xu et al. (9). This method uses a robust standard error and controls for unequal follow-up time, as well as

quantitative or multiple covariates. To aid interpretation, the risk of the primary outcome will also be estimated from the Kaplan-Meier estimate of the risk.

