### **Covariates**

All analyses (primary outcomes and secondary outcomes) will stratify on study country only (Burkina Faso or Mali).

For the primary outcome, we will also build a model adjusting for the following potential confounders:

- Age at enrolment
- Child's Sex
- Bednet use at baseline in 2017

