### **Pre-specified subgroup analyses, interactions and exploratory analyses**

As described above, the primary analysis will be pooled across the two study centres, stratified by (i.e. adjusted for) country. Efficacy (ratio and difference) measures will be presented for both sites combined. Investigation of any differences in intervention effects between the centres (formally, evidence for an interaction between intervention group and study centre) is pre-specified due to possible differences in performance of these interventions under different malaria transmission intensity. All outcomes will, therefore, also be tabulated by centre, and site-specific efficacy estimates will be presented.

Investigation of differences between study groups in each study year is also pre-specified, as described above, because it is possible that the efficacy of RTS,S/AS01 booster doses changes over time, or following successive doses. This will be assessed by exploring evidence for an interaction between intervention group and study year.

Evidence for effect modification by age at enrolment will be explored. It is possible that vaccination will perform differently according to the extent of prior exposure to malaria. As described above, analyses of the first four years of the study (analysis population D) will be conducted splitting children according to their age in June 2021 (children aged 5 years or more, vs. children who were still under 5 years; younger children subsequently received an extra year of intervention).

Finally, evidence for effect modification by child's sex (observed in the RTS,S Phase III trial) will be explored by inclusion of an interaction term in the Cox models for the primary outcome over the whole analysis period (period A). Severe malaria meeting the WHO definition and malaria deaths will also be included as exploratory analyses.

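### The protocol's bed-net sub-analysis classifies children by net use reported after the season's malaria, so membership could depend on the outcome, and the SAP neither carries it forward nor drops it

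*Combined protocol and SAP*

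**What the plan says.** Protocol section 10.2, after describing the intention-to-treat and per-protocol analyses, lists further sub-analyses by age, gender and "bed net use during the transmission season, as determined by the history obtained at the cross-sectional surveys". Section 7.6.3 sets the timing: "A survey of all study children will be undertaken approximately one month after the last round of SMC administration". The SAP dates the two extension surveys as "conducted in November/December 2020 and November/December 2021". On seasonality, protocol section 4.1 reports "over 80% of cases occurring during the rainy season (July – October) and during the following month".

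The SAP handles nets differently. Under Covariates, the adjusted model for the primary outcome includes "Bednet use at baseline in 2017". The section on pre-specified subgroups and interactions covers study centre, study year ("Investigation of differences between study groups in each study year is also pre-specified"), age at enrolment and sex. Net use is not listed there, and nothing says that the protocol's sub-analysis has been withdrawn.

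**The concern.** A subgroup should rest on something fixed before the events it stratifies. Here the classifying history is taken after most of the season's episodes. A child treated for malaria may begin to use a net, or the caregiver may describe past use differently. Episode risk differs by arm: the SAP's superiority section reports incidence about 60% lower in the combined group over the first three years. Any change in reporting driven by malaria would therefore move different numbers of children in different arms, and randomisation would not protect the comparison within a net-use group. Children without a survey history fall out of the analysis, and no rule is given for them.

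At stake is the reading of absolute benefit. The SAP defines the incidence rate difference as "the cases averted per 1000 child-years at risk" and regards it as important for policy. A difference in cases averted between net users and non-users could be read as effect modification when none exists.

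**Working it through.** **Order of events.** Over 80% of cases fall in July to October and the following month, and the surveys are in November/December. The net history is thus taken when most of the season's events have happened. Some November cases and the later dry-season cases may follow it.

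**Plan's nearest figure.** The documents give no figure for the net-use subgroup. The closest is section 10.2's detectable difference of 25.9% in the year after the third booster (1367 child-years per group, 200 per 1000, 90% power). With power = Φ(|r0 − r1| / √((r0 + r1)/PY) − 1.96), r0 = 0.200 and r1 = 0.200 × (1 − 0.259) = 0.1482:

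0.0518 / √(0.3482/1367) − 1.96 = 3.25 − 1.96 = 1.29, giving power 0.90. It reproduces, so the same rate model is used below.

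**Inputs for the check**
- Incidence in the single-intervention group: 200 per 1000 (section 10.2), and 305 per 1000 (SMC alone, years 1–3, SAP).
- Rate ratio, combined versus single intervention: 0.40 (from the 60% reduction), set equal in users and non-users.
- True net use p: 50%, 80% or 90%. Assumed; section 4.1 says only that use is high.
- Share q of children with at least one episode who change their reported status: 10% to 30%. Assumed; the documents give nothing.

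**Formulas.** Let λ be the episode rate in an arm over one child-year and a = 1 − e^(−λ) the chance of at least one episode. If a share q of affected non-users report use, the observed rates are:
- non-users: λ(1 − q) / (1 − qa)
- users: λ[p + (1 − p)q] / [p + (1 − p)qa]

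For the reverse change, exchange the two groups and replace p by 1 − p.

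**Worked case** (200 per 1000, p = 0.8, q = 0.2). The chance a is 0.1813 at λ = 0.20 and 0.0769 at λ = 0.08.
- Non-users: 0.16/0.9637 = 0.1660 and 0.064/0.9846 = 0.0650. Averted: 101 per 1000.
- Users: 0.168/0.8073 = 0.2081 and 0.0672/0.8031 = 0.0837. Averted: 124 per 1000.

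**Results**

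| Incidence per 1000 | Net use | Change in report | Averted, users / non-users | Rate ratio, users / non-users |
|---|---|---|---|---|
| 200 | any | none | 120 / 120 | 0.40 / 0.40 |
| 200 | 80% | 10% of affected non-users report use | 122 / 111 | 0.40 / 0.40 |
| 200 | 80% | 20%, same | 124 / 101 | 0.40 / 0.39 |
| 200 | 80% | 30%, same | 127 / 91 | 0.40 / 0.39 |
| 200 | 80% | 10% of affected users report non-use | 111 / 152 | 0.40 / 0.42 |
| 200 | 80% | 20%, same | 101 / 179 | 0.39 / 0.43 |
| 200 | 50% | 20%, same | 101 / 137 | 0.39 / 0.41 |
| 200 | 90% | 20%, same | 101 / 225 | 0.39 / 0.47 |
| 305 | 80% | 20% of affected non-users report use | 189 / 158 | 0.40 / 0.39 |
| 305 | 80% | 20% of affected users report non-use | 158 / 252 | 0.39 / 0.44 |
| 305 | 90% | 20%, same | 158 / 297 | 0.39 / 0.49 |

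The truth is 120 averted in both groups at 200 per 1000, and 183 in both at 305 (0.6 × 305). A simpler version with season risks of 18% and 8% agrees: at 30% of affected non-users changing, non-users show 0.126/0.946 − 0.056/0.976 = 0.076, or 76 averted per 1000 against a truth of 100.

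**The case against.** The strongest reply is that the SAP governs the analysis and does not list this subgroup. Its only net variable precedes the outcome. Much of that stands: the listed SAP analyses are untouched, and the problem sits in one clause of the protocol. But the SAP does not say that the clause is withdrawn, so the survey-based definition remains the only one stated for this sub-analysis.

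A reader might go further and infer that cases averted in users and non-users will differ spuriously. The documents do not support that. It requires malaria to change net use or its reporting, for which they give neither evidence nor size. With no such change there is no bias by this route. Nor can one infer that benefit would look too small in children without nets, because the reverse change makes it look too large. No document plans cases averted by net use; the rate difference is planned overall, by year and by site. Effect modification by sex is to be tested in the Cox model, and on the ratio scale the distortion is much smaller.

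Loss of children without a survey also has no figure. Retention was 92% and 90% at the early 2019 census (protocol section 2.3.2), which suggests a modest loss but does not say who is missing.

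Finally, baseline use does not answer the clause's own question, which concerns use during the season. That is a fair cost, not a defence of a classification taken after the outcome.

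**Conclusion.** The point holds as a weakness in the protocol's definition together with a mismatch between protocol and SAP. Membership is post-randomisation and could depend on malaria. If it does, absolute effects by net use could be wrong in either direction: in the scenarios above with a 20% change in reporting, a true 120 averted per 1000 appears as 101 to 225, depending on the group, the direction of change and the level of net use. Rate ratios over all scenarios shown stay between 0.39 and 0.49 against a true 0.40. The largest shifts occur where non-users are few and affected users report non-use. These sizes rest on assumed net use, assumed changes in reporting and equal true efficacy in both groups; they show sensitivity and do not estimate bias. The primary analysis and the SAP's listed subgroups are not affected, so this is an inexpensive improvement and not a threat to the trial's conclusions.

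**What to change.** If the sub-analysis is kept, replace the survey-based wording in protocol section 10.2 with bed-net use at baseline in 2017, for all mITT children, and add the same definition to the SAP's subgroup list. Label any version based on survey-reported net use as exploratory. If it is not kept, say so in the SAP.

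The previous year's survey is a tempting definition for years 4 and 5, but it should not be the main one. It is still post-randomisation, it follows seasons in which malaria differed by arm, and for year 4 it predates the new nets issued at the start of the extension (protocol section 7.1).

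The cost is about one sentence in each document, using a variable that the SAP's adjusted model already needs. The downside is that 2017 use, recorded when children were 5–17 months old, measures use in later seasons less exactly, particularly after the new nets are issued.
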